**Hypothesis 1b:** Changes in resting plasma NPY levels and the release of NPY in response to standardized cardiopulmonary exercise testing (CPX) conducted before and after a 3-month progressive exercise-training program will correlate with improvements in self-regulation and reward sensitivity.

**Aim 2.** Evaluate whether changes in NPY correlate with changes in self-efficacy and intrinsic motivation for exercise in response to a rigorous 3-month individually tailored, exercise-training program.

**Hypothesis 2a:** At baseline, acute exercise-induced increases in plasma NPY during CPX will correlate with exercise-related self-efficacy and intrinsic motivation to exercise.

**Hypothesis 2b:** The release of NPY during CPX will increase in response to the 3-month exercise-training program and correlate with increases in self-efficacy and intrinsic motivation to exercise.

**Aim 3.** Determine whether capacities for self-regulation and reward sensitivity, as well as self-efficacy and intrinsic motivation for exercise change in response to the 3-month exercise-training program and predict exercise maintenance.

**Hypothesis 3:** At endpoint, the factors under investigation will significantly predict exercise maintenance.

**Aim 4.** Evaluate whether changes in NPY system function across the 3-month exercise-training program correlate with improvements in pain sensitivity and interference, as well as depressive and PTSD symptoms.

**Hypothesis 4a:** At baseline, CPX-induced increases in plasma NPY will not correlate with pain-related interference and sensitivity, depression or PTSD severity.

**Hypothesis 4b:** At endpoint, CPX-induced increases in plasma NPY will correlate with reductions in pain-related interference and sensitivity, as well as with reductions in depression and PTSD symptoms.

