### A. Development of a Non-Pharmacological Approach to Treating CP/PTSD

The National Institute of Health (NIH) and the Veterans Health Administration (VHA) has emphasized the importance of developing novel, non-pharmacological approaches to CP management. As many as one half to three quarters of patients who present for PTSD treatment have a significant CP condition. Conversely, among persons presenting for treatment of CP, approximately 20% to 37% have PTSD. In addition, substantial research suggests that the co-prevalence of CP and PTSD negatively impacts the course of both disorders, such that individuals who experience both conditions report greater pain, affective distress and disability than individuals with either CP or PTSD alone.

Our laboratory has been examining the possible benefits of a rigorously defined, closely monitored individually tailored and motivationally based progressive exercise-training program for the CP/PTSD population. Such health behavior change paradigms are thought to be critical to improving CP in medically and psychiatrically complex populations, as well as to reducing CP-related disability and dependence on medications with high potential for abuse and morbidity, such as opioids. However, although many researchers have successfully helped patients initiate regular exercise, establishment of exercise maintenance has been difficult to achieve in both general and clinical populations. The proposed R21 investigation is therefore designed to investigate the neurobiological and related neuropsychological mechanisms by which our 3-month progressive exercise-training paradigm may foster exercise maintenance.

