### B. Exercise-Training Induced Augmentation of NPY System Function May Mediate Benefits in CP/PTSD

Research in rodents and humans shows that severe chronic or life-threatening stress reduces baseline plasma and central nervous system NPY levels. Effects of stress on NPY in humans and rodents are, however, individually variable. For example, exposure to extreme stress had minimal effect on NPY levels among “selected” Special Forces soldiers compared to “unselected” trainees over 3-4 weeks of selection training. In addition, NPY levels achieved at peak stress during survival training correlated negatively with dissociation and distress, and positively with military performance thought to rely on frontal lobe function. In contrast, Vietnam Veterans with severe chronic PTSD had low resting plasma NPY levels and blunted NPY responses to sympathetic system activation. Cerebrospinal fluid (CSF) NPY was also low in combat veterans with PTSD when compared to either healthy non-traumatized controls or combat-exposed healthy controls. Of note, higher resting plasma NPY was associated with decreases in PTSD symptom severity retrospectively assessed over time, and with improvements in PTSD symptoms assessed across a wait-list controlled clinical trial whether or not the active PTSD treatment was received.

Exposure to traumatic stress can lead to noradrenergic system hyperreactivity, which is the most replicated neurobiological finding across clinical studies of PTSD. As previously detailed, norepinephrine (NE) released in the prefrontal cortex (PFC) at high levels during intense stress diminishes PFC-mediated working memory, executive function and inhibition of the amygdala. NPY moderates the release of NE. Under conditions of low to moderate stress, resting levels of NPY *restrain* NE release from peripheral sympathetic neurons and in brain by activating NPY-Y2 pre-synaptic receptors. This moderates arousal and facilitates calmness. During high stress, NPY is released from sympathetic neurons and in brain; peripherally released NPY also crosses the blood brain barrier. In the brain, NPY counters the anxiogenic effects of corticotropin releasing hormone in the amygdala. In the periphery, NPY is rapidly metabolized to NPY3-36, a selective NPY-Y2 receptor agonist that

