## APPROACH

**Overall Strategy:** The proposed research will assess effects of a rigorous, individually tailored 3-month progressive exercise training in patients with CP/PTSD on NPY system function during a standardized cardiopulmonary exercise test (CPX) as related to changes in pain sensitivity, depression and PTSD, reward sensitivity and self-regulation, and TTM motivational constructs related to exercise maintenance.

**Participant Characteristics, Recruitment Strategies, Screening Evaluation:** See Human Subjects section.

**Scheduling of Women:** Each cold pressor and CPX session in women will be scheduled 2-6 days after the start of menses during the early follicular phase (when estrogen and progesterone levels are low and stable), or after initiation of a new pill cycle in women on oral contraceptives. Women on other types of steroid contraception will be scheduled as convenient as steroid levels are generally constant.

Measures	Eligibility Screening Session	Baseline Resting CPT	Baseline CPX/CPT	Midpoint Resting CPT	Post-Train Resting CPT	Post-Train CPX/CPT	F/UP 1 & 3 Month
Baseline Dx Status							
SCID-5, LEC-5, CAPS-5	X						
BAT-L	X						
Pain Ratings							
WHYMPI- Interference	X		X	X		X	X
Numerical Rating Scale	X	X	X	X	X	X	X
Cold Pressor Test		X	X	X	X	X	
Psychiatric Symptoms							
BDI-II, PCL-5/CAPS-5	X		X	X		X	X
CSSRS	X			X		X	
Exercise Behavior							
TTM Stage Change	X		X	X		X	X
Exercise Motivation							
TTM Self-Efficacy/ SDT EMS	X		X	X		X	X
Executive Function & Self-Regulation							
Go/No-Go Task			X			X	
Generalized Self-Efficacy			X	X		X	X
Emotion Regulation Scale			X	X		X	X
Reward Sensitivity							
TEPS & EEfRT			X	X		X	X
Blood Biomarkers	X	X	X	X	X	X	

1. *Structured Clinical Interview for DSM-5 (SCID)-5:* This current gold-standard clinician-administered interview will be used to diagnose psychiatric and substance abuse disorders except for PTSD (see below).

2. *Life Events Checklist (LEC-5):* The LEC-5 will be used to code exposure to potential traumatic experiences and serve as a reference for the CAPS-5 assessment.

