**Cold Pressor Test (CPT):** Per standard CPT procedures, participants will hold their right hand, up to the wrist, in a temperature controlled ice water bath, while keeping the hand still. They are instructed to say when they first experience pain and to withdraw their hand when the pain becomes intolerable. Pain threshold is defined as the number of seconds between hand immersion and the first report of "pain." Pain tolerance is defined as the number of seconds between hand immersion and hand withdrawal from the water. To prevent risk to subjects, a 7-minute time limit for immersion, unknown to the patient, is imposed. The CPT is performed just before and 30' after CPX testing to assess effects of acute exercise on pain sensitivity. To assess effects of exercise training on resting pain sensitivity, the CPT also will be performed 1-

2 days before each CPX and at the exercise-training midpoint. At these sessions, participants will engage in the same procedures (except the CPX) at the same time of day as those performed at the CPX sessions.

**Progressive Exercise Training Program:** After the initial CPX and CPT sessions, participants return to the CSU for 2 exercise-training sessions with our exercise physiologist. A pre-programmed heart rate monitor that “beeps” when exercise intensity increases is provided to participants to ensure that the targeted HRR is reached in accordance with individualized progressive exercise prescriptions. After these sessions, the exercise physiologist will instruct participants to gradually increase the frequency of their prescribed exercise sessions at home (per protocol) to 3x/week by week 4. During weeks 4, 7, and 10 an investigator will call participants to check-in and discuss any barriers to exercise. Basic motivational interviewing techniques (i.e. reflective listening) and problem solving strategies (the current standard of care in this area) will be used to facilitate exercise compliance while maintaining safety. To verify home exercise, participants will wear an actigraph and heart rate monitor that measures activity and heart rate. Data from the heart rate monitor will be downloaded and reviewed with participants upon return to the clinic for test sessions.

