### Statistical Analysis Plan

**Power and Sample Size Considerations:** Power calculations were carried out based on our recently published study which measured NPY, at baseline and peak time-points, in response to a single cardiopulmonary exercise stress test (CPX). Achievement of a Cohen’s d effect size of .5 will suggest statistically and clinically significant effects of the treatment within the CP/PTSD group. Thus, in order to obtain a power of 80% at the 5% level of significance a sample size of 30 participants will be required.

**Data Analyses:** Baseline demographics and descriptive variables (e.g., age, gender, pain duration) will be summarized. Descriptive summaries for continuous variables will be presented in terms of means and standard deviations while discrete variables will be summarized in terms of relative frequencies and percentages.

**Aims 1-2 &4:** The hypotheses under Aims 1, 2 and 4 will be evaluated using unconditional latent growth models (LGMs). The approach does not assume a linear trajectory and is thus ideal for this proposal. The intercept of the LGM will be centered on the baseline self-report data (i.e., first slope loading will be fixed to 0.0). The intermittent time point (midpoint) will be freely estimated, and the final post-training time point will have a corresponding slope factor loading fixed to 1.0. Accordingly, the mean and variance of the slope factor will convey the fixed (average) and random effects (individual differences) of change across exercise training. Effects of the exercise program will be evidenced by a significant slope factor mean (indicating significant change in the metric of interest). A significant slope variance will indicate individual differences in change across training and support further investigation of predictors of the variability.

**Aim 3:** At both CPX testing time-points, the putative mechanisms under investigation (reward, self-regulation, exercise-based SE and IM) will be correlated with each other using Pearson or Spearman correlations, as appropriate. Based on these findings, these putative psychological mechanisms will be entered as predictors in a discriminant function analysis to predict exercise maintenance.

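### The SAP reads a significant slope mean in a single trained group as an effect of the exercise program; it shows only average change across training.

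*Combined protocol and SAP*

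**What the plan says.** Under Aims 1-2 & 4, the Statistical Analysis Plan fits unconditional latent growth models with the baseline loading fixed at 0, the midpoint loading free and the post-training loading fixed at 1. It describes the slope mean as average change over training, and then gives the rule: "Effects of the exercise program will be evidenced by a significant slope factor mean (indicating significant change in the metric of interest".

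The power paragraph uses similar language. A Cohen's d "effect size of .5 will suggest statistically and clinically significant effects of the treatment within the CP/PTSD group".

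Section 8.1a plans for 30 participants to enter exercise testing and training. No control, wait-list or attention group is described for this study. The healthy trauma controls mentioned with the preliminary data belong to the earlier study.

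**The concern.** The rule joins two different statements. The parenthesis is right: a significant slope mean indicates change in the measure. The main clause attributes that change to the program. With one group and no group term in the model, nothing in the analysis separates the program from whatever else happens over the same three months. The candidates are the natural course of symptoms, regression to the mean after entry on a current PTSD diagnosis, repeat testing, and contact with staff at assessment visits.

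What is at stake is the conclusion. The 5% level protects against declaring change when there is none. It gives no protection against declaring a program effect when there is change but the program did not cause it. Because the plan fixes the interpretation in advance, following it as written would carry the attribution into the results.

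**Working it through.** **1. What the slope mean estimates.** With loadings 0, λ and 1, the model-implied means are μ_I at baseline, μ_I + λμ_S at midpoint and μ_I + μ_S at post-training. So μ_S is the post-training mean minus the baseline mean. If residual variances are free (an assumption; the SAP does not say), there are 9 parameters: 2 factor means, 3 factor variances and covariances, λ and 3 residual variances. There are also 9 moments: 3 means and 6 variances and covariances. The model is just-identified and the estimated slope mean equals the observed difference in means. There is no term for a comparator.

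**2. What the plan's own sample size is for.** Inputs from the power paragraph are d = .5, 80% power, 5% level and N = 30.
- One-group test of a mean change, two-sided, normal approximation: n = ((1.960 + 0.842)/0.5)² = 31.4, so 32. The noncentral t gives 34. The stated 30 is close to the first figure.
- Two-group comparison at the same d, normal approximation: 63 per group.

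The stated N therefore fits only a single-group test of change. Whether 30 is quite enough for that is a separate matter.

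**3. Which measures the rule reaches (schedule table in Approach).**
- *Baseline, midpoint and post-training, so the rule applies as written:* pain interference, numerical pain rating, BDI-II, PCL-5/CAPS-5, TTM stage, exercise self-efficacy and motivation, generalized self-efficacy, emotion regulation, TEPS and EEfRT.
- *Also three occasions, but not self-report:* blood biomarkers and the cold pressor test. The SAP centers the intercept on self-report data, so these come under the rule only if the model is extended. The same caution applies to EEfRT, a computerized task, and to the CAPS-5 interview.
- *Two occasions only:* Go/No-Go and CPX-induced NPY release. The three-point model does not reach them.

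Of the six hypotheses under Aims 1, 2 and 4, only 2b also predicts a mean increase ("The release of NPY during CPX will increase in response to the 3-month exercise-training program"), and it concerns a two-occasion measure.

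**4. Illustration of size.** Assume the program has no effect and background change is c SD of the change score. The documents give no value for c, so the range is assumed. For a paired t test with n = 30, two-sided 5%, the critical value is 2.045 on 29 df and the noncentrality is c√30. For the growth model, assume a Wald z test with free residual variances. The standard error is then the ML SD of change divided by √n, and the test rejects when |t| > 1.960 × √(29/30) = 1.927.

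| c (assumed) | c√30 | Paired t | Wald z |
|---|---|---|---|
| 0 | 0 | 5% | 6% |
| 0.1 | 0.55 | 8% | 10% |
| 0.2 | 1.10 | 19% | 22% |
| 0.3 | 1.64 | 36% | 40% |
| 0.4 | 2.19 | 56% | 61% |

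The Wald column is the less certain. In a check on four simulated data sets the slope estimate agreed in all four. The standard error agreed in three; the exception had a slope near zero, where λ is close to unidentified.

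**The case against.** The strongest reply is that the plan already calls the slope change across training, that most of the hypotheses governed by the rule are correlational, and that a small mechanistic study needs no control arm. All three points are fair. No test or estimate would alter, and no control arm is being asked for. But the main clause of the rule still says program effects are evidenced by the result, and the parenthesis does not withdraw that.

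The plan also limits some rival explanations. Psychotropics and supportive psychotherapy must be stable for three months, there is no severity cut-off beyond diagnosis, and other CP/PTSD treatment is expected to be delayed during participation. Test conditions are standardized for menstrual phase, fasting, time of day and medication washout. These measures reduce drift and co-treatment, but do not remove natural course, regression to the mean, repeat testing or contact.

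Four stronger readings are tempting and should not be made.

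- *That nothing is measured before training except one baseline.* Pain interference, numerical pain rating, BDI-II, PCL-5/CAPS-5, TTM stage, and exercise self-efficacy and motivation are scheduled at both screening and the baseline CPX. For women the gap from screening to experimental procedures may be 2 to 4 weeks. The SAP does not use this short interval, and it is not a comparator, but it exists.
- *That the protocol's background shows improvement without treatment.* It cites "improvements in PTSD symptoms assessed across a wait-list controlled clinical trial whether or not the active PTSD treatment was received", but the sentence says that higher resting NPY was associated with improvement. Such an association can hold among untreated patients whose average change is zero, so it says nothing about mean drift.
- *That the aims and purpose statements are also wrong.* Aim 3 speaks of factors that "change in response to the 3-month exercise-training program and predict exercise maintenance"; the Overall Strategy says "The proposed research will assess effects of a rigorous, individually tailored 3-month progressive exercise training in patients with CP/PTSD on NPY system function"; the cold pressor section says "To assess effects of exercise training on resting pain sensitivity, the CPT also will be performed". A hypothesis or a purpose may be causal. The error lies in the rule for reading the result.
- *That the slope rule is the stated test of all change under Aim 3.* The SAP assigns it to Aims 1, 2 and 4, and Go/No-Go, the task chosen for self-regulation, has no midpoint.

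**Conclusion.** The point holds for the two sentences in the Statistical Analysis Plan. In this design a significant slope mean is evidence of average change over the training period and, without a comparator, not by itself evidence of a program effect. This follows from the design and the model and needs no numerical assumption.

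The size in this trial is unknown. The rates above illustrate how the rule behaves under assumed drift, and a reader should not take them as estimates of this study's error rate. They also rest on a two-sided 5% test, n = 30 with complete data and, for the Wald column, free residual variances.

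The reach is moderate. The correlational hypotheses stand as they are, and the rule as written covers only measures taken on three occasions. It is still worth correcting before analysis, because it determines what the study may conclude about the program.

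**What to change.** Change two sentences, both in the Statistical Analysis Plan.

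1. Under Aims 1-2 & 4, replace the rule with: *A significant slope factor mean indicates average change across the training period; without a control group it is not by itself evidence of an effect of the exercise program.*
2. In the power paragraph, replace the closing reference to treatment effects with: *mean change within the CP/PTSD group.*

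No participants, visits, data or models are added, and the correlational analyses are unchanged. The cost is that the study makes no stand-alone claim that the program caused the change.

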**[[contact]](mailto:[contact])**

**Statistical Plan on page 8**

## AIMS and HYPOTHESES

The assessment and treatment of chronic pain (CP) and Posttraumatic Stress Disorder (PTSD) are national priorities for the National Institute of Health (NIH) and the Veterans Health Administration (VHA) as we continue to see steep increases in the prevalence of these conditions among returning Veterans as well as relatively high rates of these conditions among civilians. Our laboratory has developed a rigorous, individually tailored, 3-month progressive exercise training program that appears to modify a key factor (neuropeptide Y: NPY) involved in the pathogenesis of CP and PTSD. Preliminary data suggest that progressive exercise-training induced changes in NPY system function were associated with improvements in PTSD, depression and pain-related interference and sensitivity, as well as intrinsic motivation to exercise. The proposed R21 will extend this research to examine the relationship between progressive exercise-training induced changes in NPY and the capacity for reward and self-regulation. These latter capacities are thought to be essential to intrinsic and extrinsic motivation and self-efficacy, which are known to promote long-term exercise maintenance, which is critical for long-term health maintenance. Findings from the study are therefore expected to inform development of more effective therapeutic interventions for CP/PTSD aimed at forestalling serious long-term disability and reliance on pharmacological interventions with high potential for abuse, dependence, and morbidity. In the proposed study, we will investigate the association between changes in key biological and neuropsychological factors induced by a rigorous, 3-month individually tailored, progressive exercise training program and achievement of exercise maintenance in a CP/PTSD population.

**Aim 1.** Evaluate whether changes in neuropeptide Y (NPY) system function correlate with changes in self-regulation and reward across the rigorous 3-month individually tailored, progressive exercise training program.

**Hypothesis 1a:** Pre-training resting plasma NPY levels will correlate with capacities for self-regulation and reward.

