#### **E. Summary of Significance**

- (1) This study will establish whether exercise-induced changes in NPY system function are associated with changes in putative mechanisms that predict exercise maintenance—a problem that has dogged proponents of exercise as a health benefit for many years. If so, exercise programs can be calibrated to optimize/maintain changes in NPY system function, to more efficiently and effectively deliver immediate and long-term health benefits to patients with CP/PTSD and reduce health care costs.
- (2) This non-pharmacological approach also could be used as an adjunct to existing cognitive-behavioral PTSD or pain therapies to enhance their efficacy—and potentially reduce progression to opiate use with the attendant risks of abuse, dependence, morbidity and death.

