**Feasibility to achieve AIMS:** Recruiting veterans can be challenging, but inclusion of non-veterans allows us to successfully carry out our studies in this area. To enhance recruitment, we both advertise and work with collaborators at affiliated institutions who refer participants. Finally, we have an experienced multidisciplinary team and infrastructure in place, which is critical to the success of our studies in this area. In [name] CDA2 study to date, there have been no dropouts once subjects begin exercise.

**Additional Considerations:** Some participants may not respond to exercise training which could spur the development of novel pharmacological approaches to address a possible inability to increase the release of NPY in response to exercise. We will collect and process additional blood at each session to enable measurement of additional relevant biomarkers of interest (e.g., neurosteroids, ACTH, inflammatory markers) as possible with additional funding by the NC-PTSD or other funding sources.

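### No primary hypothesis, testing order or multiplicity rule is set while any significant slope counts as an effect: roughly 22 to 36 hypothesis tests and 14 to 16 slope tests share an unallocated 5%

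*Combined protocol and SAP*

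**What the plan says.** The analysis rules are in one section of the combined document, the Statistical Analysis Plan.

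- **Method for Aims 1, 2 and 4:** "The hypotheses under Aims 1, 2 and 4 will be evaluated using unconditional latent growth models (LGMs").
- **Decision rule:** "Effects of the exercise program will be evidenced by a significant slope factor mean (indicating significant change in the metric of interest"). The sentence applies to whichever measure is modelled.
- **Level and size:** "in order to obtain a power of 80% at the 5% level of significance a sample size of 30 participants will be required". The basis is a Cohen's d: "effect size of .5 will suggest statistically and clinically significant effects of the treatment within the CP/PTSD group". The source is a published study of baseline and peak NPY in a single CPX. The sidedness of the 5% is not stated, and no hypothesis or endpoint is attached to it.

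AIMS and HYPOTHESES lists 1a, 1b, 2a, 2b, 3, 4a and 4b, none marked primary. Most cover several constructs. For example, 1a reads "Pre-training resting plasma NPY levels will correlate with capacities for self-regulation and reward". The measures list gives several scores for most constructs. No section sets a testing order or an adjustment for multiple tests.

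**The concern.** With many measures, no primary and a rule that accepts significant change on whichever metric is examined, a few significant results should be expected even if training changes nothing and NPY is related to nothing. The plan gives no way to separate such a result from a real one.

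Section E, Summary of Significance, raises the stakes: "This study will establish whether exercise-induced changes in NPY system function are associated with changes in putative mechanisms". A single significant result out of dozens could be reported under that sentence. The 80% power statement does not help, because nobody can say which test it describes.

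**Working it through.** **1. The plan's own figure.** For a within-group d of .5, n = ((z for alpha + z for power)/d)². At two-sided 5% and 80% power this is ((1.960 + 0.842)/0.5)² = 31.4, so 32, within two of the stated 30. Normal-approximation power at 30 is 78%. A two-sided paired t-test needs 34 and has about 75% power at 30. One-sided versions need 25 (normal) or 27 (t). So 30 roughly fits one two-sided pre-post comparison at an undivided 5%.

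**2. Counting the hypothesis tests.** These counts are built from the listed scores.

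- Self-regulation and reward, broad reading, 7 scores: Go/No-Go commission errors, generalized self-efficacy, two emotion-regulation sub-scales, two TEPS sub-scales, EEfRT.
- Narrow reading, 4 scores: Go/No-Go as the only self-regulation measure (section C presents it as the measure to relate to NPY), two TEPS sub-scales, EEfRT.
- Motivation, 2: exercise self-efficacy and intrinsic motivation.
- Pain and symptoms, 5: interference, cold pressor threshold, cold pressor tolerance, depression, PTSD.

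| Hypothesis | Broad | Narrow |
|---|---|---|
| 1a: resting NPY with each score | 7 | 4 |
| 1b: two NPY changes with each score | 14 | 8 |
| 2a: NPY release with two motivation scores | 2 | 2 |
| 2b: one increase, two correlations | 3 | 3 |
| 4a: predicts no correlation | 5 | left out |
| 4b: NPY release with five scores | 5 | 5 |
| Total | 36 | 22 |

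Aim 3 would add tests and is not counted.

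**3. Counting the slopes.** 7 + 2 + 5 + 2 NPY measures (resting, CPX release) = 16. The schedule gives Go/No-Go and the CPX no midpoint, so the three-point growth model fits 16 − 2 = 14. The increase in 2b is the NPY-release slope, so the upper counts overlap by one: 36 + 16 − 1 = 51 distinct tests.

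**4. Chance of at least one false positive.** All nulls are taken as true and each test is read at two-sided 5%.

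- Independent tests: 1 − 0.95^k.
- Test statistics with common correlation ρ: 1 − ∫ φ(u)[Φ((c − √ρ·u)/√(1−ρ)) − Φ((−c − √ρ·u)/√(1−ρ))]^k du, with c = 1.960.

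| Tests (k) | Independent | ρ = .2 | ρ = .3 | ρ = .5 |
|---|---|---|---|---|
| 14 slopes | 51% | 47% | 44% | 35% |
| 16 slopes | 56% | 52% | 48% | 37% |
| 22 hypothesis tests | 68% | 62% | 57% | 44% |
| 36 hypothesis tests | 84% | 78% | 72% | 55% |

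The expected number of false positives is 0.05k: 0.7 to 0.8 for the slopes and 1.1 to 1.8 for the hypothesis tests, whatever the correlation.

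**5. Sensitivity.** A simulation at n=30 put the correlation between outcomes rather than between test statistics. It assumed .5 between the two NPY measures and −.3 between baseline and change. At an outcome correlation of .5 it gave 71% for the 36 tests, 41% for 16 slopes and 35% for 14.

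**The case against.** Four points can fairly be made for the plan.

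- **The stated rule covers slope means only.** The hypothesis tests are nearly all correlations, and the plan gives no significance rule for those in Aims 1, 2 and 4. Unconditional growth models of single measures do not test them either, which is a separate defect. A reader might infer that the plan reads every test at an unadjusted 5%. It does not say so: the level appears once, for power, and the rest is inferred from silence. This stands as a limit on the finding. It does not supply the missing rule.
- **A count of 36 is not the only reading.** Hypothesis 4a predicts no correlation, so a significant result there contradicts it and is not a false claim of effect. Section C supports a narrower set of self-regulation scores, although the measures table lists three instruments under that heading. This stands, and a range is therefore given.
- **The slope rule alone does not make a false positive more likely than not.** A reader might infer that it does. The 14 measures that fit the model give 51% if independent and less than half at a correlation of .2. The stronger statement depends on adding the correlation tests.
- **The study is early-phase.** A reader might infer that the whole text is confirmatory. The evidence is mixed. Section 8.4 calls the work a first step, and the aims ask whether relationships exist. Against that stand section E, the power paragraph's language of treatment effects, and section 8.3, which speaks of evaluating efficacy. No test is actually labelled exploratory.

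**Conclusion.** The point holds in bounded form. The plan accepts a significant slope on any modelled metric as evidence of an effect. It names no primary, no testing order and no adjustment, and it assigns its single 5% level to no hypothesis.

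Under a global null at 5% per test, the chance of at least one false positive is 68% to 84% for the hypothesis tests if independent and 44% to 55% at a common correlation of .5. For the slopes alone the figures are 51% to 56% and about 35% to 37%. Pooling everything at the upper counts gives 1 − 0.95^51 = 93% if independent, but that rests on a decision rule for correlations that the plan never states.

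The figures assume that the counts above are right, that 5% applies to each test, and that no effect is real. With some real effects there are fewer true nulls and the chance is lower. The correlations between tests are assumed, because the documents give none.

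**What to change.** Before analysis, name one primary hypothesis in the SAP and tie both "at the 5% level of significance" and N=30 to it.

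A suitable candidate is the pre-to-post change in CPX NPY release (hypothesis 2b). It has no midpoint measurement, so it needs a paired comparison, not the three-point growth model. Power must be restated: about 75% for a two-sided paired t-test at d=.5 and n=30. The d must also be justified for change across training, because the cited basis is the response within a single CPX. The sponsor may prefer an association as primary. In that case 80% power at n=30 requires r of about tanh((1.960 + 0.842)/√27) = .49.

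For everything else:

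- Label it secondary or exploratory.
- Report 95% confidence intervals and Benjamini-Hochberg-adjusted p-values within each aim.
- State that this controls false discovery rate, not family-wise error. Under a global null, one primary plus three adjusted aims still gives about 1 − 0.95⁴ = 19% if independent.
- Say that a significant slope on a secondary metric does not by itself establish an effect, and soften the section E wording to match.

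The cost is SAP text and adjusted p-values, with no added participants or visits. The downside is that fewer secondary results will reach significance at n=30. Bonferroni over all 36 tests would cost more: paired-t power at d=.5 would fall from 75% to 24%.
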